Official title of the Study:

Omega 3 Fatty Acids in Patients with Chronic Kidney Disease

NCT Number

NCT03280615

Date of the Document

July 31, 2019

Material and methods:

We invited to participate patients with Chronic Kidney Disease (CKD) who had a urine albumin excretion of 30 mg/g creatinine or over. All these participants were part of Non-communicable Chronic Disease programs at public primary health care clinics of East Metropolitan Santiago. Participants were invited to a first interview to assess their eligibility for the study. We excluded participants younger than 18 years and older than 85 years of age. We also excluded those who had chronic debilitating diseases such as active cancer, heart failure grade III or more according to the classification of the New York Heart Association¹, chronic debilitating infections or a history of drug or alcohol abuse. In the case of diabetic patients, we excluded those who were decompensated, defined as a fasting blood glucose over 150 mg/dl or a glycosylated hemoglobin over 8%. The study was approved by the ethics committee of East Metropolitan Santiago Health Service.

Participants deemed eligible were cited after an overnight fast to the outpatient clinic of the Institute of Nutrition and Food Technology (INTA). After signing an informed consent, they were subjected to the following procedures:

1. Weight, height and waist circumference were measured.
2. A fasting blood sample was obtained to measure blood glucose, serum lipids, glycosylated hemoglobin, creatinine, cystatin C, β 2 microglobulin, C reactive protein, interleukin-6 and fatty acid profile in red cell membranes. Cystatin C and interleukin 6 were measured using ELISA kits from R&D Systems. Red cell membrane fatty acids were measured by liquid chromatography after extracting lipids from erythrocytes using Bligh y Dryer² method and subsequently derivatized. All other determinations were carried out using routine clinical laboratory methods in a certified clinical laboratory (Vida Integra).

3. A spot urine sample was obtained to measure albumin, creatinine and urea nitrogen at Vida Integra laboratory.
4. Blood pressure and pulse wave velocity were measured using a Mobil-O-Graph® oscillometric device. Augmentation pressure and index and reflection magnitude of the pulse wave are also measured. The measurements were done in the sitting position after a five minutes rest in a quiet room.
5. Measurement of carotid intima media thickness using a General Electric LogiQ ultrasonographic device with border detection software. A 14.2 x 47 mm lineal GE 12L-RS transducer was used. International measurement norms were used ³.
6. Measurement of liver fat infiltration using the same ultrasonographic device but with a convex multifrequency (2 – 5.5 MHz) 4C RS GE transducer. Fatty infiltration was ascertained using Hamaguchi score ⁴. We have previously validated this technique against liver fat measurement using magnetic resonance spectroscopy.

Participant features were reassessed with the new laboratory determinations and those who continued to comply with inclusion criteria were randomized into two groups, balancing by gender, age, body mass index and urine albumin excretion expressed per mg of creatinine. Randomization was carried out using an iteration software based on random number generation. The output was an individual number for each patient. This number was sent to the oil manufacturer, who had the codes for each number and prepared the supplement to be used.

1. Active supplement contained 282 mg of docosahexanoic and eicosapentanoic acids per ml.
2. Placebo supplement: Contained corn oil

Participants were instructed to drink 13 ml of the supplement per day in one or two doses. Both supplements had a lemon flavor and were indistinguishable due to deodorization technology used

to prepare them. Therefore the investigators and the participants were blinded to the treatment allocation.

The intervention period lasted 3 months. Participants were cited every two weeks to provide them with a new bottle of supplement. They returned the used bottle and the residual content was measured to determine compliance. They were also interrogated about adverse events or other eventualities.

At the sixth week and at the end of the intervention at 12 weeks, participants were subjected to the same assessments done at baseline.

All participants could call the investigators in any moment if they an intercurrent problem. If a subject failed to attend an appointment, he or she was called by phone or visited at their houses to find out the reason for not showing. If a subject declined to continue in the study, he or she was considered as a loss from follow up.

Data analysis:

Until the end of the intervention period for all participants, they were only identified with their allocation number. Once the intervention ended, each participant was classified as pertaining to group 1 or 2, without knowing which was the group receiving the active supplement. All red cell membrane fatty acid composition measurements, was analyzed when all statistical analysis of the rest of the variables were done, to maintain the blinding. An intention to treat analysis was performed.

Normality of variable distribution was analyzed using Shapiro Wilk test. Since most variables had a non-normal distribution, results are expressed as median (interquartile range). By the same token, non-parametric statistical methods were used to compare variables. Chi square or fisher tests were used to compare proportions. Differences between groups were compared using Kruskal

Wallis test. To assess changes in repeated measures of a single parameter a mixed linear regression model for repeated measures was used⁵. Significance level was set at 0.05

The main outcome of the study was set as a reduction in urine albumin excretion by 20% or more. We anticipated that 35% more participants receiving the active product than those receiving placebo would attain this reduction. Thus, the sample size to obtain results with an α of 0.05 and a power of 0.8 was 38 participants per group.

Results:

Participant flow is shown in figure 1. We randomized 50 participants per group and lost five in corn oil group and four in Ω -3 group. The demographic features, body mass index and baseline albumin excretion of participants randomized to each group are shown in table 1. No differences between groups were observed, therefore the premises of randomization were correctly attained. Red blood cell membrane phospholipids fatty acid composition during the study are shown in table 2. Patients receiving the active supplement had significant increases in eicosapentanoic and docosahexanoic fatty acid levels.

A 20% reduction in urine albumin excretion was attained in 13 participants of group 1 and 19 participants of group 2 (fisher $p= 0.274$). The clinical and laboratory parameters in the three assessment periods for groups 1 and 2 are observed in table 3.

Summarizing, participants receiving corn oil maintained their pulse wave velocity during the follow up while controls experienced an increase in this parameter. Triacylglycerol levels decreased significantly in the Ω -3 group and glycosylated hemoglobin increased significantly in both groups

The compliance with the study product for groups 1 and 2, calculated measuring the leftovers was 88.7 (74-97) and 89.6 (77-98) %, respectively ($p= 0.99$). Eighty nine adverse events were recorded (48 in group 1 and 27 in group 2, $p = \text{NS}$). Of these, two were severe (a severe hyperkalemia and

the discovery of a cervical mass that resulted in a medullary thyroid carcinoma, both in participants of group 1). Mild gastrointestinal symptoms were reported by 12 and 14 participants in groups 1 and 2 respectively.

Preliminary conclusions:

1. The primary outcome measure of the study was not attained, since urine albumin excretion decreased by 20% or more in a similar proportion of participants in each intervention group.
2. The striking reduction in serum triacylglycerol observed in participants receiving Ω -3 fatty acids is a known pharmacological effect of Ω -3 fatty acids.
3. The deterioration of glycosylated hemoglobin in both groups, may be associated with the fact that participants received 110 Kcal/day of extra calories with the supplement.
4. The lack of increase in pulse wave velocity in group 2 may indicate that the supplement that this group received had a favorable effect on arterial stiffness.
5. The supplement was well tolerated. The lack of differences between groups in compliance and gastrointestinal complains indicates that the fish oil effectively almost completely deodorized.

[figure not shown]
Figure 1

Table 1: Initial features of randomized participants expressed as median (interquartile range)

	Gender (F/M)	Age (years)	Body mass index (kg/m²)	Urine albumin (mg/g creatinine)
Corn oil				
Group	26/24	66 (58-74)	31 (27.2-35.3)	604.5 (212-1234)
Ω-3 group	23/27	67 (56-74)	33.5 (30-37.3)	365.5 (157-1079)
Difference		NS	NS	NS

Table 2: Changes in red blood cell membrane phospholipids fatty acid composition. Values expressed as median (interquartile range) in mg/100 mg of total fatty acids

	Corn oil group (n=45)			Ω-3 Group (n=46)			p ¹
	Basal	Six weeks	Final	Basal	Six weeks	Final	
Pentadecanoic Acid (C15:0)	0.2 (0-3)	2.3 (0-3.2)	2 (0-3)	0.2 (0-2.9)	1.2 (0-3.2)	2.3 (0-3.3)	b
Palmitic Acid (C16:0)	27.4 (25.2-29.9)	28.9 (27-31.1)	25.7 (23.7-28.3)	27.8 (25.5-29.2)	28.8 (26.7-30.8)	27.7 (24.8-28.9)	
Heptadecanoic Acid (C17:0)	2.4 (0.4-4.2)	3.1 (0.8-4.7)	2.3 (0.3-4.7)	1.7 (0.4-3.6)	3.1 (0.5-4.5)	2.7 (0.5-4.3)	b
Estearic Acid (C18:0)	15.6 (12.9-18.4)	15.3 (13.7-17.1)	17.5 (13.6-18.8)	16.3 (13.8-17.9)	15.6 (14-17.9)	16.9 (14.1-18.1)	
Arachidic Acid (C20:0)	0 (0-0.3)	0 (0-0.3)	0 (0-0.3)	0 (0-0.3)	0 (0-0.3)	0.2 (0-0.3)	
Eneicosanoic Acid (C21:0)	0 (0-0)	0 (0-0)	0 (0-0)	0 (0-0)	0 (0-0)	0 (0-0)	
Behenic Acid (C22:0)	0.9 (0.6-1.2)	1.1 (0.8-1.2)	0.8 (0.3-1)	1 (0.7-1.2)	1.1 (0.9-1.3)	0.9 (0.4-1.2)	
Lignoceric Acid (C24:0)	2.6 (1.4-3.4)	2.8 (2.4-3.4)	2.2 (1-3.4)	2.6 (1.3-3.3)	2.8 (2.2-3.3)	2.6 (0.8-3.3)	
Total Saturated	54.9 (50.7-58.3)	55 (51.9-57.7)	55.8 (51.7-59.8)	54.1 (49.7-58.2)	55.2 (50.1-57.8)	55.9 (52.9-62.2)	b
Miristoleic Acid (C14:1)	0 (0-0)	0 (0-0)	0 (0-0)	0 (0-0)	0 (0-0)	0 (0-0)	
Pentadecanoico Acid (C15:1)	0 (0-0)	0 (0-0)	0 (0-0)	0 (0-0)	0 (0-0)	0 (0-0)	
Palmitoleic Acid (C16:1)	0 (0-0.4)	0 (0-0.4)	0 (0-0.4)	0 (0-0.4)	0 (0-0.4)	0 (0-0.3)	
Cis 10-Heptadecanoic A Acid (C17:1)	0 (0-0)	0 (0-0)	0 (0-0)	0 (0-0)	0 (0-0)	0 (0-0)	
Oleico Acid (C18:1)	14.3 (13.3-15.7)	14.7 (13.7-15.7)	13.7 (12.1-14.5)	14.7 (13.3-15.9)	14.8 (14-16.1)	14.2 (13-15)	
Gadoleic Acid (C20:1)	0 (0-0.2)	0 (0-0.2)	0 (0-0.2)	0 (0-0.2)	0 (0-0)	0 (0-0.2)	
Erucic Acid (C22:1)	0 (0-0)	0 (0-0)	0 (0-0)	0 (0-0)	0 (0-0)	0 (0-0)	
Nervonic Acid (C24:1)	2.5 (1.5-3.1)	2.7 (2.3-3.2)	2.2 (1.7-2.7)	2.6 (1.7-3)	2.8 (2.4-3.2)	2.5 (0.9-2.8)	
Total monounsaturated	17.4 (16.2-19)	17.5 (16.9-19)	16.6 (15.3-18.5)	17.6 (16.3-19)	17.7 (17.2-19)	17.4 (15.3-18.1)	
Linoleic Acid (C18:2 n6 c)	11.8 (9.3-13.9)	12.2 (10-13.9)	11.8 (8.6-13.4)	10.9 (9.4-12.6)	11 (9.5-12.3)	9.9 (8.5-11.5)	
Gama linolenic Acid (C18:3 n6 c)	0 (0-0)	0 (0-0)	0 (0-0)	0 (0-0)	0 (0-0)	0 (0-0)	
Alfa linolenic Acid (C18:3 n-3)	0 (0-0.2)	0 (0-0)	0 (0-0.1)	0 (0-0.1)	0 (0-0)	0 (0-0.1)	
Eicosadienoico Acid (C20:2)	0 (0-0.3)	0 (0-0.3)	0.1 (0-0.3)	0 (0-0.3)	0 (0-0.3)	0 (0-0.2)	
Table 2 continuation							
	Corn oil group (n=45)			Ω-3 Group (n=46)			p ¹
	Basal	Six weeks	Basal	Six weeks	Basal	Six weeks	

Dihomo gamalinolenic Acid (C20:3 n-6)	1.5 (1.1-1.9)	1.4 (1.1-1.7)	1.4 (1-1.9)	1.3 (0.8-1.9)	1.1 (0.8-1.5)	1.2 (0.7-1.6)	
Cis-11-14 icosatrienoico Acid (C20:3 n-3)	0 (0-0)	0 (0-0)	0 (0-0)	0 (0-0)	0 (0-0)	0 (0-0)	
Arachidonic Acid (C20:4 n-6)	9.4 (6.1-12.5)	10.1 (6.2-12.1)	9.1 (6.4-12.6)	8.9 (5.5-11.7)	8.8 (6.6-11.1)	8.1 (5.1-10)	
Eicosapentanoic Acid (C 20:5 n-3)	0.4 (0-0.7)	0.4 (0-0.7)	0.5 (0.2-0.8)	1.3 (0.4-3)	2.8 (1.4-3.3)	2.6 (1.1-3.5)	c
Docosadienoico Acid (C22:2)	0 (0-0)	0 (0-0)	0 (0-0)	0 (0-0)	0 (0-0)	0 (0-0)	
Docosahexanoic Acid (C22:6 n-3)	1.9 (1.3-2.8)	1.8 (1.4-2.6)	1.6 (1-2.4)	2.7 (2-3.7)	2.9 (2.2-3.8)	2.8 (2.2-4.2)	c
Total polyunsaturated	27.5 (23.4-30.8)	26.6 (24.1-30.3)	26.6 (22.4-29.9)	27.6 (23.2-31.5)	27 (24.3-31.4)	26.1 (22.1-29.9)	b

^a = significance for differences between groups determined by a mixed effects lineal regression model for repeated measures. ^b = difference between groups without intervention effect, ^c= intervention effects without differences between groups ^c= intervention effect with differences between groups (Ω -3 fatty acid effect)

Table 3: Measured parameters in both treatment groups, expressed as median (interquartile range)

	Corn oil group (n=45)			Ω-3 Group (n=46)			p [†]
	Basal	Six weeks	Final	Basal	Six weeks	Final	
Clinical parameters							
Systolic blood pressure (mm Hg)	129 (121-142)	134 (123-140)	133 (123-150)	135.5 (126-153)	137 (122-150)	138.5 (128-149)	
Diastolic blood pressure (mm Hg)	81 (73-87)	80 (73-86)	83 (74-90)	81.5 (73-95)	80.5 (75-92)	84.5 (74-93)	
Weight (kg)	76.4 (69.7-91.5)	77.4 (71.7-90.5)	77.6 (70.1-93.3)	90.4 (79.1-101.2)	91.05 (77.5-100.5)	91.2 (77.6-101.9)	
Waist circumference (cm)	104 (97-113.2)	104 (97.6-114)	105 (96-113)	110.5 (103.5-122.4)	112 (104.2-120)	111.25 (104-120.6)	
Carotid intima media thickness:							
Left (mm)	0.66 (0.6-0.83)	0.67 (0.57-0.84)	0.71 (0.58-0.83)	0.71 (0.61-0.88)	0.735 (0.62-0.85)	0.695 (0.59-0.82)	
Right (mm)	0.62 (0.55-0.715)	0.62 (0.54-0.73)	0.645 (0.555-0.755)	0.68 (0.6-0.78)	0.7 (0.61-0.78)	0.71 (0.61-0.79)	
Arterial stiffness measures							
Augmentation pressure (mm Hg)	8 (5-12)	9 (5-15)	12 (5-19)	9 (5-16)	11 (6-20)	12 (4-18)	b
Augmentation index (%)	18 (9-29)	23 (11-35)	25 (14-39)	20 (8-31)	27 (12-38)	23 (9-34)	b
Reflection magnitude (%)	66 (61-73)	70 (59-75)	69 (57-75)	67 (61-73)	67 (63-73)	66 (61-74)	
Pulse wave velocity (m/s)	9.3 (8.5-10.7)	9.7 (8.3-11)	9.7 (8.3-11.2)	9.75 (8.1-10.6)	10 (7.6-10.8)	10.1 (8-10.9)	c
Liver ultrasound							
Liver steatosis score (units)	3 (2-4)	3 (2-4)	3 (3-4)	3 (2-4)	4 (2-4)	3 (3-4)	
Laboratory values							
Fasting glucose (mg/dl)	94 (86-115)	97 (89-120)	95 (86-132)	99 (83-118)	107.5 (90-143)	103.5 (90-137)	
Total cholesterol (mg/dl)	165 (138-203)	162 (135-195)	160.5 (134-195)	170 (140-204)	167.5 (141-203)	154.5 (127-176)	
Hdl cholesterol (mg/dl)	43.1 (37.1-52.3)	44.2 (36-51.6)	41.7 (35.3-53.2)	41.3 (35.2-54.4)	42.7 (35.6-53.8)	41.55 (37.8-51.8)	
Triacylglycerol (mg/dl)	147 (117-219)	133 (96-220)	150 (106-219)	163.5 (111-238)	125.5 (90-173)	117.5 (90-167)	c
Serum creatinine (mg/dl)	1 (0.82-1.76)	1.09 (0.79-1.78)	1.08 (0.81-2.06)	1.01 (0.79-1.33)	0.98 (0.75-1.57)	1.04 (0.8-1.37)	
Urine albumin excretion (mg/L)	370.6 (140.9-756.2)	344.3 (132.1-1096.5)	513.9 (185.4-978.7)	375.35 (146.5-584.4)	360.85 (162.9-1099.6)	467.9 (144.6-1005.2)	
Blood urea nitrogen (mg/dl)	22.3 (16.7-36.7)	20.5 (16.3-37.5)	20.7 (16.1-36.9)	18.95 (15-25.5)	19.6 (15.4-28.6)	19.15 (13.6-28)	
Urine creatinine excretion (mg/dl)	78 (56-100)	95 (69.5-113.5)	80 (57-118)	91.5 (62-135)	99.5 (62-126)	90.5 (68-121)	
Glycosylated hemoglobin (%)	5.9 (5.4-6.7)	6.2 (5.4-6.8)	6.2 (5.6-6.9)	6.35 (5.7-7.2)	6.45 (5.8-7.2)	6.5 (5.9-7.4)	b
Urine albumin/creatinine ratio (mg/g)	541 (173-1125)	561.5 (129-1063)	678 (149-1217)	363 (157-1030)	435 (164-950)	492 (129-1071)	

Table 3 continuation

	Corn oil group (n=45)			Ω-3 Group (n=46)			p [¶]
	Basal	Six weeks	Final	Basal	Six weeks	Final	
Urine urea nitrogen (mg/dl)	569.6 (439.3-784.2)	570.5 (467.95-783.4)	615.6 (433.6-803.3)	629.45 (526.6-824.9)	659.4 (444.6-881.3)	594.1 (488.3-763.6)	
C Reactive protein (mg/L)	1.68 (1.11-4.11)	1.81 (0.99-4.49)	1.91 (0.99-5.22)	3.265 (1.54-5.27)	2.5 (1.31-5.35)	2.14 (1.15-5.85)	
β2 microglobulin (mg/L)	2.7 (1.9-5.1)	2.7 (2-5)	2.4 (2-5.1)	2.35 (1.8-3.4)	2.3 (1.8-3.8)	2.2 (1.7-3)	
Interleukin-6 (pg/ml)	0.3 (0.2-0.4)	0.3 (0.2-0.3)	0.2 (0.2-0.4)	0.3 (0.2-0.4)	0.3 (0.2-0.4)	0.3 (0.2-0.4)	
Cistatin-C (mg/L)	1 (1-1.9)	1.1 (1-2.1)	1.2 (1-1.8)	1.1 (0.9-1.6)	1.2 (1-1.8)	1.2 (0.9-1.6)	
Estimated glomerular filtration rate (ml/min/1.73 m ²)	68 (31.2-80)	67 (28.6-75.9)	60.1 (34.6-76.5)	60.7 (42.4-81.9)	58.5 (33.7-73.9)	60.6 (39.6-78.9)	

[¶] = significance for differences between groups determined by a mixed effects lineal regression model for repeated measures. ^a = difference between groups without intervention effect, ^b= intervention effects without differences between groups ^c= intervention effect with differences between groups (Ω-3 fatty acid effect

References:

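### The primary outcome cuts a skewed albumin measure to a yes/no 20% fall without naming the visit or the measure, and no between-group albumin estimate with an interval supports the null conclusion

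*Combined protocol and SAP*

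**What the plan says.** Procedure 3 under Material and methods describes one urine sample per assessment: "A spot urine sample was obtained to measure albumin, creatinine and urea nitrogen at Vida Integra laboratory". The assessments are repeated: "At the sixth week and at the end of the intervention at 12 weeks, participants were subjected to the same assessments done at baseline". A participant with complete follow-up therefore has three values.

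The Data analysis section fixes the endpoint: "The main outcome of the study was set as a reduction in urine albumin excretion by 20% or more". It does not name the deciding visit. Nor does it say whether the 20% applies to albumin concentration (mg/L) or to the albumin/creatinine ratio (mg/g); Table 3 reports both.

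The sample size follows from the same endpoint: "We anticipated that 35% more participants receiving the active product than those receiving placebo would attain this reduction", so that "the sample size to obtain results with an α of 0.05 and a power of 0.8 was 38 participants per group". In the event, "We randomized 50 participants per group" is reported, and the trial "lost five in corn oil group and four in Ω -3 group", leaving 45 and 46. The 20% fall was "attained in 13 participants of group 1 and 19 participants of group 2", Fisher p = 0.274.

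The same section says that most variables were non-normal and that repeated measures were assessed with a mixed linear regression model. Table 3 gives both albumin measures at all three visits under that model. Neither row carries a significance letter. No log transformation, between-group estimate or confidence interval is given for albumin.

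**The concern.** A 20% cut treats a fall of 19% like a doubling, and a fall of 21% like a fall of 80%. With a baseline interquartile range of 173 to 1125 mg/g, the measure suits a log-scale analysis, and a yes/no version throws away much of what each sample says.

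Two things are at stake. The first is power: a worthwhile reduction could be missed by the responder test and found in the same samples analysed continuously. The second is interpretation: conclusion 1 infers from a non-significant Fisher test that the proportions were alike, and gives no interval for the difference. The undefined visit and measure add to this, because a reader cannot reproduce the 13 and 19 or tell whether another choice would change them.

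**Working it through.** **1. The plan's own figures.** Fisher's exact test on 13/45 versus 19/46 gives p = 0.2737, matching 0.274. Reversing the denominators (13/46 versus 19/45) gives 0.192, and 13/50 versus 19/50 gives 0.284. So group 1 is the arm of 45 (corn oil), and the test used the 91 participants remaining, not the 100 randomised. For the sample size, a 35-point absolute difference, two-sided 0.05, power 0.80 and a continuity correction give 36 to 37 per group for control rates of 25% to 40%. That is within two of 38, but the control rate is assumed because the plan states none.

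**2. What the responder result supports.** 13/45 = 28.9% and 19/46 = 41.3%, a difference of 12.4 points. SE = sqrt(0.289×0.711/45 + 0.413×0.587/46) = 0.099. The 95% CI is 12.4 ± 1.96×9.9, or -7.0 to 31.9 points.

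**3. Inputs for the power comparison.**
- Total log SD, from the corn oil baseline quartiles in Table 3: ln(1125/173)/1.349 = 1.39. The omega-3 quartiles (157, 1030) give the same.
- Sizes: 45 and 46.
- Assumed: a true 25% lower ratio, effect ln(1/0.75) = 0.288; a 25% upward drift in both arms; response judged at week 12 on mg/g.
- Assumed: within-person log SD s from 0.3 to 0.6, since the documents give none.

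**4. Worked case, s = 0.4.**
- Control responders: Φ((ln 0.8 − ln 1.25)/(√2×0.4)) = Φ(−0.446/0.566) = 21.5%. Active: Φ((−0.446 + 0.288)/0.566) = 39.0%. Simulated Fisher power is 40%.
- Baseline-adjusted log ratio: correlation (1.39² − 0.4²)/1.39² = 0.917. Residual SD = 1.39×sqrt(1 − 0.917²) = 0.554. SE = 0.554×sqrt(1/45 + 1/46) = 0.116. Power = Φ(0.288/0.116 − 1.96) ≈ 70%; simulation gives 69%.

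**5. Simulated power over the range.**

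| Within-person log SD | Responder, Fisher | Log ratio, week 12 |
|---|---|---|
| 0.3 | 58% | 90% |
| 0.4 | 40% | 69% |
| 0.5 | 28% | 51% |
| 0.6 | 18% | 37% |

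Repeat simulations agree to within about two to three points.

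**6. Does the ordering need noise?** No. With within-person SD only 0.1 and real person-to-person change of log SD 0.6, power is about 32% for the responder test and 58% for the log analysis.

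**7. Is averaging weeks 6 and 12 safe?** Only if the effect is complete by week 6. With half the effect present then and s = 0.4, the two-visit mean has 57% power against 69% for week 12 alone.

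**8. Table 3 medians (mg/g).** Corn oil 541 to 678: 678/541 = 1.25. Omega-3 363 to 492: 492/363 = 1.36. Lower quartiles fell, 173 to 149 and 157 to 129. These are group summaries, not paired changes.

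**The case against.** The best reply is that albumin was analysed continuously. The mixed model used all three visits, and neither albumin row was flagged. That stands: weeks 6 and 12 were not left unused. But the absence of a letter in a table is not an estimate. No scale is stated for a variable of a kind the plan itself calls mostly non-normal, and no size or interval can be read from it.

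A second reply is that the interval's upper limit, 31.9 points, lies just below the planned 35, so the trial did answer its design question. That is fair as far as it goes, but it is not evidence that the proportions are alike.

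Three stronger readings are tempting, and the documents support none of them.

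- *Noise supplies most of the responders.* With no true change and no drift, the chance of being labelled a responder is 6% at a per-sample CV of 10%, 21% at 20%, 30% at 30% and 39% at 60%. The observed 28.9% on corn oil fits a CV near 29%. It is also of the order that real change gives: SD 0.1 within person and 0.6 between persons, with 25% drift, gives Φ(−0.446/0.616) ≈ 23%. The control rate cannot separate the two.
- *Albuminuria rose in both arms and the conclusions hide it.* The rises of 25% and 36% compare unpaired medians, the lower quartiles fell, and the trial's own model flagged no change over time. The figures are only indicative.
- *A log-scale model should now become the main efficacy estimate.* The responder result is known and null. Promoting another analysis at this point would be a post-hoc change of primary outcome, which labelling does not cure. Nor is there reason to expect the result to turn positive.

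**Conclusion.** The point holds as one about lost information, an incomplete endpoint definition and a missing estimate. Under the stated assumptions, the week-12 log analysis has about 30 points more power than the responder test at SD 0.3 and about 20 more at SD 0.6. The absolute figures depend on an assumed within-person SD, effect and drift. The ordering held at every SD tried and when the change was real rather than noise.

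Conclusion 1 is supportable as a failure to show a difference, not as a finding of similar proportions. How much of either arm's responder rate is measurement variation cannot be settled from the documents, though the three samples per participant could help to estimate it. The point affects how the result is reported and does not overturn it.

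**What to change.** - Keep the 20% responder count as the stated primary outcome. State which visit and which measure (mg/L or mg/g) define response, and report the difference in proportions with its 95% CI.
- Add a supportive analysis, labelled as added after the result was known: a baseline-adjusted model of log albumin/creatinine (mg/g), with weeks 6 and 12 as repeated measures and a group-by-visit term. That term lets the effect differ between visits, so a full effect by week 6 is not assumed.
- From it, report the week-12 ratio of geometric means with 95% CI, and beside it the median within-person percent change per arm.
- Word conclusion 1 from that interval, saying which effects the data exclude and which they do not.

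The cost is one extra model on data already held, with no new samples or visits. The downside is that it is post hoc: it can inform the reading of the primary result but cannot replace it.

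### The primary responder comparison is a crude Fisher test that uses neither the four factors the allocation was balanced on nor diabetes status; the cost is precision and protection against chance imbalance, not bias.

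*Combined protocol and SAP*

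**What the plan says.** Under Material and methods, the eligibility text sets a rule for one subset only: "In the case of diabetic patients, we excluded those who were decompensated". Decompensation is defined as "a fasting blood glucose over 150 mg/dl or a glycosylated hemoglobin over 8" per cent.

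After the laboratory reassessment, "those who continued to comply with inclusion criteria were randomized into two groups, balancing by gender, age, body mass index and urine albumin excretion", the last taken relative to urine creatinine. Diabetes is not among these factors.

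Under Data analysis, the method for a binary outcome is one sentence: "Chi square or fisher tests were used to compare proportions". No stratum or covariate is stated there, and the mixed model for repeated measures has no stated diabetes term.

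Under Results, the baseline description is limited: "The demographic features, body mass index and baseline albumin excretion of participants randomized to each group are shown in table 1". Table 1 has no diabetes row, and no table gives the number of diabetic participants in either arm. The primary result reads: "A 20% reduction in urine albumin excretion was attained in 13 participants of group 1 and 19 participants of group 2", with a Fisher p of 0.274. No risk difference or confidence interval is given.

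The only indirect evidence on the diabetes mix is in Table 3, for the 45 and 46 participants analysed. Basal HbA1c is 5.9 (5.4-6.7) on corn oil, and the omega-3 row reads "6.35 (5.7-7.2) 6.45 (5.8-7.2) 6.5 (5.9-7.4"), of which the first entry is basal. Basal fasting glucose is 94 (86-115) and 99 (83-118) mg/dl.

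**The concern.** There are two gaps, and the first does not depend on diabetes. The investigators judged gender, age, BMI and albuminuria important enough to build into the allocation, and the primary test then sets them aside. An analysis that ignores the balancing factors gives up whatever precision they carry. Baseline albuminuria matters most here, because the outcome is a percentage fall from that same baseline. Even with balancing, the Table 1 medians are 604.5 against 365.5 mg/g for albuminuria and 31 against 33.5 kg/m² for BMI, both reported as not significant.

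The second gap is diabetes. The entry rule could not be applied without classifying candidates as diabetic or not, but the reader never learns how the two kinds of patient fell between the arms. If the chance of a 20% fall in albuminuria over 12 weeks differs by diabetes status, a chance imbalance would shift the crude difference in this sample. The reader also cannot tell what mix of diabetic and non-diabetic kidney disease the null albuminuria result describes.

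**Working it through.** **1. Reproduce the primary result.** Inputs: 13 and 19 responders (Results); 50 per arm less five on corn oil and four on omega-3 leaves 45 and 46 (Results and table headers).

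- Two-sided Fisher on 13/45 against 19/46: p = 0.2737, which matches the stated 0.274 with group 1 as corn oil.
- Alternatives do not match: 13/50 against 19/50 gives 0.284; 13/46 against 19/45 gives 0.192.

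The primary test is therefore the plain two-by-two comparison of 91 participants.

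**2. Effect size that goes with it.** Risk difference = 19/46 - 13/45 = 0.413 - 0.289 = 0.124.

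SE = √(0.413 × 0.587/46 + 0.289 × 0.711/45) = 0.099.

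95% CI = 0.124 ± 1.96 × 0.099 = -0.070 to 0.319, from unrounded values.

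**3. What the HbA1c figures suggest.** Take 6.5% as an assumed marker of diabetes and a normal upper half: s = (Q3 - median)/0.6745; share = 1 - Φ((6.5 - median)/s).

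- Corn oil: s = (6.7 - 5.9)/0.6745 = 1.186; share = 1 - Φ(0.506) = 0.306.
- Omega-3: s = (7.2 - 6.35)/0.6745 = 1.260; share = 1 - Φ(0.119) = 0.453.

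The gap is about 15 points. As counts, this is roughly 14/45 against 21/46, Fisher p = 0.20.

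**4. The same method on fasting glucose**, with an assumed cut-off of 126 mg/dl.

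- Corn oil: s = (115 - 94)/0.6745 = 31.1; share = 1 - Φ(1.028) = 0.152.
- Omega-3: s = (118 - 99)/0.6745 = 28.2; share = 1 - Φ(0.9585) = 0.169.

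The gap is about 2 points. Cut-offs from 110 to 130 mg/dl give gaps of about 1 to 4 points. The two markers named in the entry rule do not tell the same story.

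**5. How likely is a chance imbalance?** With 50 per arm and an assumed diabetes prevalence of 30% to 70%, the hypergeometric probability of a gap of 10 points or more is about 0.28 to 0.32, and of 20 points or more about 0.05 to 0.07.

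**6. What it could do to the estimate.** Shift = gap in diabetes share × gap in responder rate between diabetic and non-diabetic participants. The second factor is not in the documents; 10 to 30 points is assumed.

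- HbA1c-based gap: 0.15 × 0.10 = 0.015 to 0.15 × 0.30 = 0.045.
- Gap of 20 points with the largest assumed responder gap: 0.20 × 0.30 = 0.06.
- Glucose-based gap of 1 to 4 points: 0.01 × 0.10 = 0.001 to 0.04 × 0.30 = 0.012.

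**7. Tipping point.** With 13/45 fixed, 22/46 (+6.5 points) gives p = 0.085, 23/46 gives 0.054 and 24/46 gives 0.033. Significance needs five more omega-3 responders, 5/46 = 10.9 points. None of the shifts in step 6 reaches that.

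**8. Room for a model.** Responders: 13 + 19 = 32. Treatment plus four balancing factors is five slopes, 32/5 = 6.4 responders each. Adding diabetes makes six, 32/6 = 5.3.

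**The case against.** A reader might infer that the omega-3 arm held more diabetic participants and that the primary result is biased. The documents do not support that. Allocation was randomised, so diabetes is balanced in expectation and the Fisher test stays valid. HbA1c measures control as much as diagnosis: controlled diabetic patients may lie below 6.5%. The 15-point gap is within chance, the other marker in the same rule shows almost none, and Table 3 covers the 91 analysed, not the 100 randomised.

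A reader might also infer that the entry rule created a mixed population. It did not. It is a control limit for diabetic patients; a trial in albuminuric kidney disease without a diabetes restriction would enrol both groups anyway.

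It can further be said that four balancing factors rather than five is a design preference, that no passage says diabetes was stored as a study variable, that a six-slope model strains 32 responders, and that a covariate chosen once the result is known has limited value. These points stand, and they shape the fix.

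They leave the main gap in place: the primary comparison ignores the factors used in the allocation, and the split of diabetes between arms cannot be checked.

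**Conclusion.** The point holds as a matter of precision, protection against chance imbalance, and reporting. The primary comparison omits the four balancing factors and diabetes, and gives a p-value without an effect estimate. The crude difference is 12.4 points (95% CI -7.0 to 31.9), an interval too wide to show that the proportions are similar.

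Neither bias nor an uneven diabetes split is established. The shift of about 1.5 to 4.5 points rests on two assumptions from outside the documents: 6.5% HbA1c as a marker of diabetes, and a responder-rate gap of 10 to 30 points by diabetes status. Its direction is unknown. Under those assumptions the non-significant conclusion is not expected to change. The gain in precision from adjusting for the balancing factors cannot be computed, because the documents do not relate those factors to response.

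**What to change.** - Keep the Fisher test as the primary comparison. Report beside it the crude risk difference with its 95% CI.
- Add a responder comparison adjusted for gender, age, BMI and baseline urine albumin/creatinine, expressed as a standardised risk difference with 95% CI. Use one term per factor and a penalised (for example Firth) logistic fit, given 32 responders.
- As a sensitivity analysis labelled post hoc, add diabetes status; if it was not recorded as a variable, use baseline HbA1c.
- Add diabetes status by arm to Table 1 for all 100 randomised, if it was recorded. Give any responders/N by arm and diabetes status as descriptive only: 32 responders over four cells cannot show to which patients the null result applies.
- In any further randomisation, consider entering diabetes among the balancing factors and name the adjusted analysis in advance.

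Cost: two short models, plus one table row if diabetes status was recorded; baseline HbA1c was collected in any case. The downsides are a covariate chosen after the result was known and few events per parameter, so the adjusted results should support the Fisher test, not replace it.
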